The benefits of a HFib diet are supported extensively in the literature. Fiber protects against increasing body weight³⁰⁻³³, promotes fat loss³⁴⁻³⁹, increases satiety⁴⁰, and improves the metabolic and inflammatory profiles^{30,41-47}. Evidence that a HFib diet can reduce body weight and fat mass independent of a reduction in energy intake was highlighted in a recent meta-analysis⁴⁸ and a RCT in adults with MetS^{49,50}. The effect is hypothesized in part to be mediated through the powerful prebiotic effect of fiber that favorably shifts the gut microbiota leading to reduced weight gain⁴⁸, inflammation⁵¹, improved metabolic profile⁵¹, and prevention of fat accrual^{34-37,51}. Our working hypothesis is that consuming a HFib diet (≥ 30 g/day) will reduce GWG and fat accretion by diluting energy density, reducing hunger thereby reducing energy intake, and changing the gut bacteria composition. Our pilot data (n=20) found a 12 wk HFib pregnancy intervention reduced Firmicutes and increased Bacteroidetes, which was associated with reduced weight gain and fat accretion⁵². Current fiber intake of pregnant women is 17.3 g/day⁵³, well below the recommended intake (28 g/day⁵⁴), and triggering fiber to be classified as a nutrient of concern⁵⁵. Thus, increasing fiber intake has high potential for impact. However, RCTs in pregnant women are lacking to understand if this is an effective intervention strategy.

The project objective is to block randomize n=56 pregnant women to either a HFib diet or usual care. Eighteen weekly lessons will educate women on eating a HFib diet. To ensure fiber intake is met, daily snacks (10-12 g/day) will be provided. Weight gain, fat accretion, and stool microbiota will be measured twice during pregnancy (pre- and post-intervention) and assessed at 2 months, 6 months, and 12 months postpartum. Infant body composition will be measured at 2 weeks, 2 months, 6 months, and 12 months. The aims are:

Primary Aim 1: Assess the between group difference in maternal weight gain and fat accretion. H1: The HFib group will gain less weight and accrue less fat mass when compared to the control group.

Primary Aim 2: Compare fiber intake and dietary quality between groups. H2: The HFib group will consume more fiber and have a higher diet quality during pregnancy and postpartum.

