A5) Success of a SG intervention: In a large RCT funded by the NIH (R01 HL094575)⁵⁰ in non-pregnant adults with MetS, the effectiveness of two interventions were compared for weight loss and metabolic changes; MG vs. SG. Both groups met face-to-face (FTF) in groups for 12 sessions over three months. The MG followed the American Heart Association dietary guidelines and the SG focused all lessons on achieving dietary fiber (no calorie or PA goals) intake ≥ 30 g/day. At 12 months, the MG group lost -2.7 kg, while the SG group lost -2.1 kg and both groups saw improvements in dietary quality, insulin resistance, lipids, inflammation, glucose levels and blood pressure. Both groups decreased kcal/d, however the MG group had a greater decrease (-464 versus -200 kcal at 12 months). Olendski⁴⁹ tested the effectiveness two simple messages in a three group design: 1) calorie restriction + high fiber, 2) calorie restriction + low saturated fat and 3) MG intervention (a combination of restricted kcals, high fiber, and low fat). The intervention lasted 3 months with biweekly FTF individual meetings with a Dietitian. At six months, no between group difference was found for body weight lost; -7 lbs for MG, -9.1 lbs for fiber and, -10.2 lbs for saturated fat group. All groups improved dietary quality and cardiometabolic parameters. At six months, 83% of the fiber group were confident they could stick to their diet, whereas only 60% and 33% were confident in the saturated fat and MG groups, respectively ($p=0.008$). Taken together, no clear between group differences were found between a SG dietary fiber intervention and a MG intervention. This suggests in non-pregnant adults, both intervention types were effective.

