C7i) Process evaluation: Data will be collected throughout the intervention to assess barriers to recruitment and study retention, participant acceptability and intervention adherence, and how well the intervention was implemented. Participants that drop will be contacted and asked to complete a brief interview to provide feedback. Semi-structured interviews will be conducted at the final assessment (34 wks). Participants will be asked about their perception of the intervention including both positive and negative aspects and any challenges that were encountered, pros and cons of using group video counseling to promote healthy behaviors during pregnancy, and their overall satisfaction with the intervention. Interviews will be audio recorded and transcribed verbatim. Comments will be coded, categorized into themes and used to refine and further develop future interventions.

C7j) Safety monitoring: All subjects will be given a body weight scale and report body weight weekly. This allows close supervision of progression of each participant to ensure the intervention is not overly effective and all women are gaining adequate body weight. If a woman gains or loses more than 5 lbs over a two-week period, she will be flagged and contacted. If she is in the Hfib group, total weight gain recommendations will be reviewed and her dietary habits and fiber intake will be reviewed and reinforced. Rapid weight changes or any other safety concerns will be reviewed by our study physician for safety purposes. The participant's provider will be notified if physician deems necessary.

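### The C7j safety contact reinforces fiber even when a high-fiber participant is flagged for losing weight: a minor flaw, cheaply fixed by splitting the response by direction

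*Combined protocol and SAP*

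**What the plan says.** C7j states why weekly weights are collected in both groups: "to ensure the intervention is not overly effective and all women are gaining adequate body weight". The trigger works in both directions: "If a woman gains or loses more than 5 lbs over a two-week period, she will be flagged and contacted". For a flagged woman in the HFib group, the content of the contact is then set out in one sentence with two parts. First, "total weight gain recommendations will be reviewed"; second, "her dietary habits and fiber intake will be reviewed and reinforced". The section goes on: "Rapid weight changes or any other safety concerns will be reviewed by our study physician for safety purposes". Her own provider is told if the physician thinks it necessary.

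Two other places restate the rule. C5d (Monitoring & Compliance) says participants are contacted after a 5 lb change either way over two weeks, and gives no content for the contact. The opening paragraph of Protection of Human Subjects uses the same threshold as C7j. There, diet habits and fiber intake are reviewed, with no mention of reinforcing them, and the woman is asked whether she wants a report sent to her obstetrician. None of the three places gives a separate response for loss.

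**The concern.** The rule exists partly to catch an intervention that works too well, and a two-week loss of more than 5 lb in pregnancy is the clearest signal of that. Yet the response written for that signal includes encouraging the behavior under test. The Specific Aims hypothesize that the diet "will reduce GWG and fat accretion by diluting energy density, reducing hunger thereby reducing energy intake". If that is right, reinforcing fiber pushes intake downward in a woman who has been flagged because her weight is falling.

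What is at stake is the content of one safety contact. No endpoint, analysis or sample size depends on it. The protocol does treat the event as a possible harm: item (7) under Risks to Human Subjects limits recorded adverse events to excessive weight gain or loss and allergic reactions to the study food, assessed in the HFib group only. The instruction for responding to it should at least point the right way.

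**Working it through.** The protocol gives no figure to reproduce, so the check is mainly textual, with a little arithmetic for scale.

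1. **Trigger and response.** C7j has one trigger covering gain and loss and one HFib response. Nothing in C7j, C5d or Protection of Human Subjects makes the response depend on direction. The reinforcing instruction therefore applies to a loss as written.

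2. **What reinforcing means here.** C7j does not define it, but the protocol uses the word elsewhere for encouraging a behavior. Table 2 in C4 lists feedback and reinforcement as a weekly behavioral strategy, and C5c says physical activity will be mentioned but not reinforced. Reading the C7j wording as encouragement toward the fiber goal is consistent with that usage.

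3. **Direction of the expected effect.** The Specific Aims expect less hunger, lower energy intake and less weight gain. A5 cites a fiber-only arm with no calorie goal, in non-pregnant adults with metabolic syndrome, that reduced intake by 200 kcal/day and lost 2.1 kg at 12 months. For a gain, reinforcing fiber fits the aim of the contact. For a loss, it does not.

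4. **Size of a flagged loss.** 5 lb × 0.4536 kg/lb = 2.27 kg in 14 days. Against the cited arm, 2.27 / 2.1 = 1.08: a flagged woman has lost in two weeks slightly more than that arm had lost at 12 months. The populations differ, so this indicates scale only, but it suggests that fiber alone is unlikely to be the main cause.

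5. **Size of the dietary push.** The goal is 30 g/day and C5c gives the pregnancy reference intake as 28 g/day: 30 − 28 = 2 g/day above the recommendation. Measured from average intake, the change is larger: 30 − 17.3 = 12.7 g/day using the Specific Aims figure, or 30 − 15 = 15 g/day using the C5c figure.

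6. **How many women.** The documents give no rate of flagged loss. The only ceiling is the size of the HFib group, 56 / 2 = 28 if allocation is 1:1 (an assumption). With arms differing by one block of 10, it is (56 − 10)/2 = 23 to (56 + 10)/2 = 33. These count women in the arm, not women flagged.

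7. **Safeguards already present.** These are review of weight gain recommendations, study-physician review and possible provider notification (C7j); the offered obstetrician report (Protection of Human Subjects); and four-weekly adverse event assessment with immediate report to the principal investigator (item (7)). Two are less than automatic. C7j does not say that every 5 lb flag counts as a rapid change, and the obstetrician report depends on the woman's agreement.

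**The case against.** The strongest reply is that no harm has been shown. The hypothesis concerns smaller gains, not losses. C5c removes the calorie goal deliberately, as the known driver of weight loss. The goal is close to the recommended intake, and a loss of this size probably has another cause. Read as a whole, the contact begins with weight gain recommendations, which would steer a woman who is losing toward gaining, and what is reinforced includes her general diet as well as fiber. A physician then looks at rapid changes. All of this stands, and it is why the point is minor.

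It does not remove the point. Fiber intake is named among the things to be reinforced, no text exempts a loss, and the physician review follows the instruction without replacing it.

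A reader might go further and infer that the protocol leaves women who are losing weight unprotected, or that the fiber goal would cause or deepen a flagged loss. The documents do not support either. The safeguards in step 7 are real, and the conflict is inferred from the protocol's own hypothesis; nowhere does the protocol say that fiber worsens a loss. A reader might also take Protection of Human Subjects to repeat the flaw. It does not, since it asks only for review.

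A fair practical objection is that changing C7j alone would achieve little. Under C5c a dietitian telephones any woman below her fiber goal to plan an increase, and that call could reach the same woman in the same week. The fix has to cover it.

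**Conclusion.** The point holds as a cheap improvement of minor severity. As written, C7j gives a woman flagged for loss the same contact content as one flagged for gain, and the fiber part of it runs against the rule's stated purpose. This rests on two assumptions: that staff would take reinforcing to mean encouraging the fiber goal, and that the protocol's hypothesis about the direction of the fiber effect is right. The number of women affected is unknown; the 28 in step 6 (range 23 to 33) is a ceiling and should not be read as an estimate. The existing reviews limit the consequence, and no trial result depends on it.

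**What to change.** Split the C7j sentence by direction:

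- **Flagged gain:** keep the present response.
- **Flagged loss:** review weight gain recommendations and the adequacy of overall intake; send the case to the study-physician review already named in C7j; hold fiber encouragement until that review is done, both at this contact and in any C5c dietitian call about a missed fiber goal.

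Add a line to C5c so that the dietitian knows of the hold. Protection of Human Subjects contains no error to correct; a cross-reference to C7j is enough. The weekly lessons and the snacks continue unchanged.

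The change needs no new visit, staff, data item or analysis, only the protocol's usual ethics approval for an amendment. Its downside is a short delay in fiber encouragement for a woman flagged for loss, ending when the physician has reviewed her case.

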Ideally, women would enter pregnancy at an appropriate body weight. However pre-conception interventions have yet to be tested, proven viable, or successful. Many primary care physicians do not counsel patients on weight loss, diet, and exercise due to inadequate resources and feelings of ineffectiveness⁷⁰. This highlights the importance of interventions during pregnancy. Pregnancy is an important time period that “programs” disorders and a time when many pregnant women are more likely to adopt healthy behaviors for the well-being of their baby¹⁴. Several interventions have been completed with varying success and are discussed below.

A2) Intervention lack of success: Four meta-analyses^{16,18,20,24} and five systematic reviews^{15,22-25} show limited success in published interventions. For interventions including diet and physical activity (PA), three⁷¹⁻⁷³ found improvement in rate of adherence to IOM guidelines while ten⁷⁴⁻⁸³ did not see improvements in adherence. Studies compared differences by BMI groups and found effectiveness in normal weight but not overweight/obese participants^{84,85}. Two studies in obese pregnant women provided counseling with a Registered Dietitian at one session⁸⁶ or 10 sessions⁸⁷ focusing on diet and found improved dietary quality⁸⁷ and reduced GWG^{86,87}. The greatest success (80% gained <10.6 kg) was found in a study of overweight/obese women using personalization of diet and PA (walking program using pedometers) and consistent self-monitoring⁷². This study was especially impressive as the intervention started at 16-20 wks and the entire cohort had already gained excessively.

A3) Lessons from prior studies: Failed studies cite poor outcomes were due to PA not being desirable during pregnancy⁷⁹, needing one provider delivering counseling to ensure consistent messages⁷⁴, the intervention was not intensive enough^{75,84,85}, too infrequent of contact^{75,79,84}, the need to emphasize caloric restriction⁸⁴, the intervention started too late⁷⁸ or was too short⁷⁹, the need to involve significant others⁷⁶, and poor adherence^{75,81}. Successful studies were intensive, set calorie and PA goals and used self-monitoring²⁰.

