C2) Population to be studied: Women between 9 to 19 weeks pregnant with a BMI 18.5 – 45.0 kg/m² and between the ages of 18-45 years will be recruited from the University of Kansas Medical Center (KUMC) OB clinics. We will enroll all race/ethnic groups. Participant's routine OB care will be managed by their primary Obstetrician. Any interventions, laboratory or other evaluations, and decisions regarding delivery will be made by the primary Obstetrician. Groups of 6-10 subjects will be block randomized to control or the intervention group to ensure adequate size for optimal group dynamics. The intervention will start at 12-20 wks and last 18 weeks, ensuring intervention completion by 38 weeks in pregnancy. We will screen women to determine the current dietary fiber intake. If they are consuming 25 g/day of fiber or more, they will be excluded from the study. Women who do not have internet and phone access will be excluded from the study. Participants must be willing to consume provided snacks. Participants will also be excluded if they have history of gestational diabetes (GDM), diabetes, pre-eclampsia, hypertension, heart disease, hypothyroidism, or other metabolic abnormalities, current hyperemesis gravidarum, eating disorder, smoking, or are pregnant with multiples. Women that develop any of these medical conditions during pregnancy will be accounted for in the final analysis. Deviations from inclusion criteria will be at the discretion of the PI.

C3) Recruitment: We have access to the electronic clinic schedule, therefore we have the exact date and time of the recruit's OB visit. We have worked directly with physicians and staff providing an in service at meetings to ensure a smooth recruiting process so that we do not impede clinic flow. Annually, 1800 women are managed in the OB clinics at KUMC. Additionally, we will recruit using an electronic flyer via social media. Individuals who have agreed to future contact from previous studies will also be approached if eligible via email or phone.

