C7t) Breastmilk analysis: Participants who choose to breast feed will be asked to pump one breast until empty, homogenize the breastmilk by stirring, and return 20-mL to the study team for nutrient analysis. Participants will be asked to do this at 1 month, 2 months, 3 months, 4 months, 5 months, and 6 months, freeze it, and return it to the study team at the 2-month and 6-month visits. The remainder of the breastmilk collected can be kept by the participant and fed to their infant. Any leftover sample after initial nutrient analysis will be banked for future evaluations related to nutrition and brain health and KUMC.

C8) Steps to maximize adherence and retention: We will be using incentives for study visits, incentives for reporting goals, and regular short-term performance and feedback.

C8a) Incentive system: Participants will be compensated \$100 for each of the 6 study visits: baseline, end intervention, 2 weeks postpartum, 2 months postpartum, 6 months postpartum, and 12 months postpartum totaling up to \$600 for completion of all visits. Participants asked to return for repeat infant DXA (no more than 2 at each study timepoint) will be compensated an additional \$50. Compensation will be provided on a ClinCard, which is given at enrollment. After each visit study staff will load their unique card number with the respective pay. Participants can use the card anywhere Mastercard is accepted, and study staff does not have access to where the money will be spent.

C8c) Monitoring retention: When participants miss a session or reporting of behaviors, they will be contacted and a standardized protocol according to attendance and adherence demands will be used to make every effort to retain the participant or encourage reporting. This will be documented and used for program evaluation.

C9) Statistical analysis: The purpose of this study is to attain feasibility data therefore the small sample size does not afford the power to detect significance but to identify promising trends and relationships.

Analysis for Aim 1 H1: A t-test will be used to determine if there is a difference in maternal weight gain and fat accretion between the two groups.

Analysis for Aim 2 H2: A t-test will be used to quantify if there is a difference in fiber intake and dietary quality between the two groups.

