The women will be informed that the purpose of the study is to determine if a high fiber diet can help them gain the right amount of weight during pregnancy and that they will be placed in an intervention or control group. They will be told that if they participate in the study, regardless of their group assignment, that they will need to be seen two times during their pregnancy and four times after pregnancy. Further, they will be told if they are randomized to the intervention group they will be required to attend weekly video calls and report goals weekly to the study coordinator for 18 weeks.

Consent forms and HIPPA disclosure information per IRBs will be given to all subjects and their signatures witnessed. The consent forms will include a description of the study, nature of the data collection, the potential benefits and adverse reactions anticipated. Women will be assigned to group by random assignment provided by study statistician. The subjects will be told that their usual care would not be changed, withdrawn, or reduced if they chose to withdraw from the study at any time. The research team personnel will abide by all tenets of the University confidentiality policies, as well as the Privacy Protection for Research Subjects. All research staff will remain current in their NIH required Human Subjects protection and HIPAA certification.

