We are targeting recruitment of pregnant women who have a pre-pregnancy BMI 18.5 – 45.0 kg/m². We are specifically targeting women at high risk of excessive GWG during pregnancy. Data show 56% of women gain excessively^{3,4}. Excessive gestational weight gain (GWG) is associated with poor outcomes. Based on our data, we anticipate the following distribution among the 3 pre-pregnancy weight categories selected (BMI <24.9 = 40%; BMI 25-25.9 = 34%; BMI >30 = 26%). Due to the adverse health that is related to excessive GWG, it is imperative to seek interventions to prevent excessive GWG.

Data Safety and Monitoring Plan

Data security: All participants will be assigned a non-identifiable subject number. Data collected will be kept in [name] locked research laboratory. Only study personnel and [name] have keys to access this area. Electronic data will be kept on a password protected computer in [name] laboratory on the shared drive. Only personnel approved by HSC and on the protocol will have access to the data.

Data and safety monitoring plan: Monitoring will be handled by the PI and the research team.

INCLUSION OF WOMEN, MINORITIES, AND CHILDREN

Inclusion of Women: We are targeting pregnant women who have a pre-pregnancy BMI 18.5 – 45.0 kg/m². We are specifically targeting women at high risk of excessive GWG during pregnancy and at high risk of retaining a significant amount of body weight postpartum. Data show 56% of women gain excessively^{3,4} and that excessive gestational weight gain (GWG) is associated with poor outcomes.

Inclusion of Minorities: We are including all racial/ethnic groups in this study. There will be no exclusion criteria based on race or ethnicity.

Inclusion of Children: The study will include offspring born to women participating in the study.

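### Primary Aim 1 is tested by an unadjusted t-test; a prespecified model with BMI and gestational age would cost almost nothing and may improve precision, though the documents do not show by how much.

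*Combined protocol and SAP*

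**What the plan says.** Section C9 gives the whole Aim 1 analysis in one sentence: "A t-test will be used to determine if there is a difference in maternal weight gain and fat accretion between the two groups". The only covariate-adjusted method in C9 is a repeated-measures ANCOVA for the microbiome aim, and its covariates are not named.

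On design, the Specific Aims state: "The project objective is to block randomize n=56 pregnant women to either a HFib diet or usual care". C2 adds: "Groups of 6-10 subjects will be block randomized to control or the intervention group to ensure adequate size for optimal group dynamics". The human-subjects section says only: "Women will be assigned to group by random assignment provided by study statistician". No allocation ratio or stratification factor appears.

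The population is wide. C2 recruits "Women between 9 to 19 weeks pregnant with a BMI 18.5 – 45.0" kg/m². Under Importance of Knowledge to be Gained, "we anticipate the following distribution among the 3 pre-pregnancy weight categories selected", with shares of 40%, 34% and 26%. On timing, C2 says: "The intervention will start at 12-20 wks and last 18 weeks, ensuring intervention completion by 38 weeks in pregnancy". C7a computes GWG as the weight at 34 weeks minus the measured baseline weight. Table 4 places the end-of-intervention visit at 30 to 38 weeks.

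**The concern.** Pre-pregnancy BMI and gestational age at baseline are both fixed before treatment. The case report form described under Adequacy of Protection Against Risks already holds pre-pregnancy weight, height and the estimated due date. If either variable predicts gain, two things follow for a trial of this size. The t-test leaves explainable variance in the error term. And the single estimate obtained will carry whatever imbalance the randomisation happens to leave, since nothing in the allocation restrains it.

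Aim 1 states a directional hypothesis, and C11 makes positive results the trigger for the next study. A chance shift of around 1 kg could create or hide the kind of signal the trial is looking for. If an imbalance is noticed only at the end, adjusting for it becomes a post hoc choice that is open to challenge.

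**Working it through.** **Inputs from the documents.** N = 56 (Specific Aims). Pilot GWG from Table 1: usual care 18.4 ± 7.3 kg (n = 9), intervention 11.8 ± 4.0 kg (n = 14). BMI mix 40/34/26%.

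**Assumed.** Individual 1:1 allocation, so 28 per arm with no dropout; two-sided 5%; pilot SDs apply to this trial's GWG.

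**Plan's own figures.** N = 56 comes without alpha, power, effect size or SD, so it cannot be reproduced. The pilot p = 0.010 can: the pooled t-test on Table 1 gives t = 2.81, p = 0.0105. The pooled SD is therefore a reasonable reading of the pilot:

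SD = √[(8 × 7.3² + 13 × 4.0²)/21] = √30.21 = 5.50 kg.

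**Unadjusted half-width.** t(54) × SD × √(2/28) = 2.005 × 5.50 × 0.267 = 2.94 kg. It is 2.14 kg at SD 4.0 and 3.91 kg at SD 7.3.

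**BMI scenarios.** The documents give no mean gain by BMI category, so three sets are assumed for the 40/34/26% mix. Middle set: the mean is 0.40 × 14 + 0.34 × 12 + 0.26 × 9 = 12.02 kg. The between-category variance is 0.40 × 1.98² + 0.34 × 0.02² + 0.26 × 3.02² = 3.94, so R² = 3.94/30.21 = 0.130.

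**Adjusted half-width, two covariates.** Allowing for the cost of estimating them, the ratio to the unadjusted width is [t(52)/t(54)] × √(1 − R²) × √(1 + 2/51) = 1.0203 × √(1 − R²). Only BMI's R² is credited; gestational age is counted as a cost.

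**Chance BMI imbalance.** SD of the shift = √(between-category variance × 2/28 × 56/55); the 95% range is ±1.96 times this.

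| Assumed means (kg) | Variance | R² | Adjusted half-width (kg) | Change in width | Imbalance shift, 95% range (kg) |
|---|---|---|---|---|---|
| no association | 0 | 0 | 3.00 | 2.0% wider | 0 |
| 14/13/11 | 1.43 | 0.047 | 2.93 | 0.4% narrower | ±0.63 |
| 14/12/9 | 3.94 | 0.130 | 2.80 | 4.8% narrower | ±1.05 |
| 15/12/8 | 7.73 | 0.256 | 2.59 | 12.0% narrower | ±1.47 |

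Break-even is R² = 1 − 1/1.0203² = 0.039, a multiple correlation of about 0.20.

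**How often imbalance occurs.** 26% of 56 is about 15 women above BMI 30. By the hypergeometric distribution, the arms differ by 5 or more such women in 22.7% of randomisations.

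**Validity of the t-test.** In 20,000 simulated trials at each of three BMI–outcome correlations (0, 0.3, 0.5), the unadjusted test rejected a true null in 5.4%, 5.4% and 5.0% of runs, and the mean estimate stayed within 0.02 kg of zero.

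**Gestational age.** With a fixed 34-week weight, the window runs from 34 − 20 = 14 to 34 − 12 = 22 weeks. Assume uniform entry (SD 8/√12 = 2.31 weeks) and 0.3 to 0.6 kg per week. Window length then has an SD of 0.69 to 1.39 kg in gain, about 2% to 6% of 30.21, and chance shifts of about ±0.4 to ±0.7 kg. With the 30-to-38-week visit of Table 4, baseline plus 18 weeks, the window is roughly constant and most of this disappears.

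**The case against.** The strongest reply is that nothing is broken. A t-test in a randomised trial is unbiased and holds its error rate, C9 declares a feasibility study without power, and the benefit rests on assumed inputs. Most of this stands.

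- A reader might infer that the unadjusted estimate is biased, or that the 0.6 to 1.5 kg shift comes on top of the 2.94 kg half-width. Neither is so: the interval already contains chance imbalance.
- A reader might take the interval to be wider than necessary as a matter of fact. The BMI figures in A1 are rates of excessive gain classified against guidelines, not kilograms gained or fat accrued. They give neither the size nor the direction of the assumed means.
- In A2 the protocol reports: "Studies compared differences by BMI groups and found effectiveness in normal weight but not overweight/obese participants". That describes effect modification in other interventions. A main-effect covariate does not address it, so it is no support for this fix.
- The pilot SD may not carry over. Table 1 does not say how pilot GWG was measured, and its usual-care mean of 18.4 kg is well above the 12 to 13 kg implied by the scenarios. At SD 7.3, R² falls to 0.03, 0.07 and 0.15, and the two-covariate model changes the width by +0.7%, −1.8% and −5.7%.
- No figure can be given for fat accretion, the other half of Aim 1.

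The feasibility label does not remove the point. C9 still tests a directional hypothesis, and the change needs only wording.

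**Conclusion.** The point holds as a low-cost improvement in precision, with medium confidence. The Aim 1 analysis is unadjusted and no stratification factor is named. Under the stated assumptions (28 per arm, SD 5.5 kg, BMI explaining 5% to 26% of variance), adjustment narrows the GWG interval by between 0.4% and 12%. If the covariates predict nothing, it widens the interval by about 2%. The larger practical benefit is a prespecified answer to an imbalance that could account for 0.6 to 1.5 kg of the observed difference in a single trial. The documents do not support calling the t-test invalid, the estimate biased, or the loss of precision established.

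**What to change.** Replace the Aim 1 sentence in C9 with prespecified linear regression.

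- **GWG:** arm, continuous pre-pregnancy BMI, and gestational age at the baseline weight.
- **Fat-mass change:** arm, baseline fat mass, and gestational age at baseline. BMI is optional here because it overlaps with fat mass. Baseline four-compartment fat mass uses bone mineral measured postpartum (C7g, C7h), so it is not wholly a pre-treatment value. State in advance that BMI takes its place where baseline fat mass is missing or doubtful.
- **Reporting:** the adjusted difference with its 95% CI as primary, and the t-test as a check.

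Reconcile the 34-week weight in C7a with the 30-to-38-week end visit in Table 4, because this sets how much gestational age matters. Do not add a mixed model of the weekly home weights over weeks 20 to 30. A woman starting at 12 weeks would contribute intervention weeks 8 to 18 and one starting at 20 weeks would contribute weeks 0 to 10, which changes the estimand.

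The cost is a few lines of analysis wording, two or three degrees of freedom, and about 2% of interval width for GWG if the covariates prove uninformative. No new data are needed.
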